8.4 Analyses

The following will be analyzed separately by cohort, and by treatment group within the expansion cohort.

8.4.1 *Demographics and Baseline Characteristics*

Frequency distributions of gender, race and ECOG status will be tabulated. Summary statistics for age, body weight, height and body mass index will be tabulated.

8.4.2 *Efficacy Analyses*

Individual tumor responses will be listed by treatment and study day. Bone marrow blast and its percent change from baseline will be listed.

In addition, for the expansion cohort, best overall response prior to the initiation of any alternative therapy (including any subsequent ulocuplumab 800 mg for subjects in the LDAC alone arm) will be tabulated. The rate of subjects with complete remission (CR/CRi) will be summarized by a

binomial response rate and corresponding two-sided 95% exact CI using the Clopper and Pearson method. The combined rate of subjects with responses of either CR or CRi or PR will similarly be summarized.

OS and DoR will be summarized descriptively using Kaplan-Meier methodology. Median values of OS, along with two-sided 95% CIs using the Brookmeyer and Crowley method considering a log-log transformation, will be calculated.

8.4.3 Safety Analyses

All recorded adverse events will be listed and tabulated by system organ class, preferred term and treatment. Vital signs, clinical laboratory test results and any significant physical examination findings will be listed and summarized by treatment. ECG readings will be evaluated by the Investigator and abnormalities, if present, will be listed. To assess the effects of ulocuplumab on heart rate, PR, QRS, QT, QTcF, and Δ QTcF intervals the frequency distribution for maximum QTcF, PR, QRS and the maximum Δ QTcF will be tabulated. For QTcF a linear regression of Δ QTcF on drug concentration will be estimated. Summary statistics will be tabulated for all ECG parameters and changes from baseline. The plots of mean and mean changes from baseline versus time or ulocuplumab concentration may be provided. A two-sided 90% confidence interval will be constructed for the population mean of Δ QTcF at each time point.

8.4.4 Immunogenicity Analyses

Immunogenicity status will be reported relative to baseline as ADA negative, ADA positive, and positive baseline. Listings for ADA positive response will be provided by treatment.

8.4.5 Pharmacokinetic Analyses and Receptor Occupancy

Summary statistics will be tabulated for the PK parameters and RO (expansion cohort only) listed in [Section 8.3.2](#) by treatment and study day. For PK, geometric means and coefficients of variation will be presented for C_{max}, AUC and CL. Medians, minimum, and maximum will be presented for T_{max}. Means and standard deviations will be provided for the remaining PK parameters. Individual as well as mean concentration-time plots will be depicted.

The distribution of C_{trough} concentrations will be summarized using descriptive statistics by treatment and study day. To assess the attainment of steady state, geometric mean C_{trough} values will be plotted by treatment and study day.

Changes of CXCR4 RO is related to the dose and exposure of ulocuplumab. The association between the percent of RO and ulocuplumab serum concentration in peripheral blood and, when possible, bone marrow will be explored.

8.4.6 ECG Analyses

Triplicate measurements of each serial ECG will be used to obtain an average value for each time point. These averages will be used in the listings and statistical analyses. Baseline will be defined as the time point prior to dosing on the first day of Cycle 1. Summary statistics (n, mean, standard deviation of the mean, minimum and maximum) will be provided for all ECG intervals (QT, QTcF,

QTcB, QRS, PR) and for heart rate and changes relative to baseline in ECG intervals and heart rate, per day and time point.

A two-sided 90% confidence interval will be constructed for the population mean of Δ QTcF at each time point. (Change from baseline in QTcF is assumed to follow a normal distribution.) The frequency distribution of QTcF and Δ QTcF will be calculated for each sampling point on Cycle 1 Day 1 and Cycle 2 Day 15. The categories for the frequency distribution will be (≤ 450 msec, 451- 480 msec, 481- 500 msec, > 500 msec) for QTcF and (≤ 30 msec, 31- 60 msec, > 60 msec) for Δ QTcF. ECG analyses will be conducted on the ECG evaluable population. These analyses will be summarized separately for each cohort.

[REDACTED]

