4.6.1.1 Treatment Discontinuation Criteria

Subjects will discontinue study treatment upon development of following ulocuplumab-related AEs:

- Prolonged bone marrow suppression (≥ 56 days)
- Grade ≥ 3 infusion reaction
- QTcF ≥ 500 msec confirmed by at least one repeat ECG.

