5.5.1 Pharmacokinetics Collection and Processing and ECG Measurements

Serial blood samples will be collected from the dose escalation cohort. Serial blood samples and time-matched ECGs will be collected from a subset of subjects in the expansion cohort (a minimum of 15 subjects per dose level, Serial PK/ECG Subset) whereas sparse blood samples will be collected in the remaining subjects (sparse sampling subset). Serum for all ADA samples will be collected within 30 minutes before dosing.

[Table 5.5.1-1](#) and [Table 5.5.1-2](#) list the sampling schedule to be followed for the assessment of PK, ECG, ADA and RO. Further details of blood collection and processing will be provided to the site in the procedure manual.

Table 5.5.1-1: Ulocuplumab PK and RO Sampling Schedule and ECG Measurements (Escalation Cohort and Expansion Cohort, Serial PK/ECG Subset)

Study Day	Time (Relative to Dosing) Hour	Time (Relative to Dosing) Hour: Min	PK Blood Sample	RO Sample	ADA Sample	ECG ^a
Cycle 1, Day 1	-1.0	-01:00				X
	0 (pre-dose)	00:00	X	X	X	X ^b
	1.0 (end of infusion) ^c	01:00	X	X		
	1.5	01:30	X			X ^b
	2.0	02:00	X			
	3.0	03:00	X			X ^b
	5.0	05:00	X			
Cycle 1, Day 2	24	24:00	X			
Cycle 1, Day 3	48	48:00	X			
Cycle 1, Day 4	72	72:00	X			
Cycle 1, Day 8	0 (pre-dose)	00:00	X	X		
	1.0 (end of infusion) ^c	01:00	X	X		
Cycle 1, Day 15	0 (pre-dose)	00:00	X	X	X	
	1.0 (end of infusion) ^c	01:00	X	X		
Cycle 2, Day 1	0 (pre-dose)	00:00	X	X	X	
	1.0 (end of infusion) ^c	01:00	X	X		
Cycle 2, Day 8	0 (pre-dose)	00:00	X	X		
	1.0 (end of infusion) ^c	01:00	X	X		
Cycle 2, Day 15	0 (pre-dose)	00:00	X	X		X ^b
	1.0 (end of infusion) ^c	01:00	X	X		
	1.5	01:30	X			X ^b
	3.0	03:00	X			X ^b

Table 5.5.1-1: Ulocuplumab PK and RO Sampling Schedule and ECG Measurements (Escalation Cohort and Expansion Cohort, Serial PK/ECG Subset)

Study Day	Time (Relative to Dosing) Hour	Time (Relative to Dosing) Hour: Min	PK Blood Sample	RO Sample	ADA Sample	ECG ^a
Cycle 3-5, Day 1 ^d	0 (pre-dose)	00:00	X	X	X	
	1.0 (end of infusion) ^c	01:00	X	X		
Cycle 3-5, Day 8 ^d	0 (pre-dose)	00:00	X	X		
	1.0 (end of infusion) ^c	01:00	X	X		
Every 4 Cycles after 5, Day 1	0 (pre-dose)	00:00	X		X	
End of Treatment			X		X	
Follow-up ^e			X		X	

^a ECG only for subjects in expansion cohort Serial PK/ECG Subset

^b 12-lead ECGs will be extracted from the Holter recorded flashcards in triplicate within a 10-minute window ending prior to the nominal ECG collection time and before PK draws

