5.6 ECG Assessments

Safety ECGs will be done for all subjects at screening, during the treatment period and during follow-up as indicated in [Table 5.1-1](#), [Table 5.1-2](#), and [Table 5.1-3](#). All required safety ECGs will be performed on 12-lead ECG equipment used by the sites, per ECG central vendor guidelines.

Serial ECGs will be obtained only from a subset of subjects in the expansion cohort (a minimum of 15 subjects per dose level, Serial PK/ECG Subset) as indicated in [Table 5.5.1-1](#) and should be obtained at each time point listed.

The subjects must be placed in a supine position for 5 to 10 minutes prior to the start of the ECG recording for both safety and serial ECGs. The recorded QTc interval will be measured with Fridericia's correction (QTcF).

All required serial ECGs will be collected on ECG holter monitor equipment provided by the ECG central vendor. The timing of the ECG data collected on the holter monitor is critical to the endpoint of the study and must be performed according the central vendor guidelines. The serial 12-lead ECGs will be extracted from the Holter recorded flashcards in triplicate within a 10-minute window ending prior to the nominal ECG collection time and before PK draws. The serial ECGs will be assessed by the ECG vendor.

The investigative site should document any deviations from the protocol or procedures related to ECG collection or serum sampling. Accurate documentation will lead to proper accounting of the cumulative data and correct final analysis.

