7.6.7 Electrocardiograms

A two-sided 90% confidence interval will be constructed for the population mean of Δ QTcF at each time point. (Change from baseline in QTcF is assumed to follow a normal distribution.) The frequency distribution of QTcF and Δ QTcF will be calculated for each sampling point on Cycle 1 Day 1 and Cycle 2 Day 15. The categories for the frequency distribution will be (≤ 450 msec, 451- 480 msec, 481- 500 msec, > 500 msec) for QTcF and (≤ 30 msec, 31- 60 msec, > 60 msec) for Δ QTcF.

The following outputs will be provided:

- Summary of ECG parameters and changes from baseline by study day (descriptive statistics [n, mean, standard deviation, min, max] for HR, QT, QTcB, QTcF, PR and QRS; 90% CI for Δ QTcF)
- Frequency distribution summary of QTcF, PR, QRS and Δ QTcF (QTcF [msec: ≤ 450 , 451 - 480, 481 - 500, > 500 ; PR [msec] : ≤ 200 , > 200 ; QRS [msec] : ≤ 120 , > 120 ; Δ QTcF [msec] : ≤ 30 , 31 - 60, > 60)
- Listing of ECG measures (QTcF, QT, QTcB, PR, QRS, Δ QTcF, drug concentrations; flagging abnormalities)
- Plot of regression of Δ QTcF on drug concentration
- Plots of mean, and mean changes from baseline, versus time or ulocuplumab concentration may be provided

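### The ΔQTcF baseline is one unspecified pre-dose time point although two ECGs are scheduled, and whole-millisecond bands leave small gaps for triplicate means

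*Protocol*

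**What the plan says.** **Baseline.** Protocol 8.4.6 reads: "Baseline will be defined as the time point prior to dosing on the first day of Cycle 1". SAP 4.2 repeats the sentence. Neither says how several pre-dose ECGs would be combined.

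**Schedule.** Table 5.5.1-1 in Protocol 5.5.1 lists an ECG at −1.0 h and another at 0 h on Cycle 1 Day 1. Protocol 5.6 says serial ECGs "should be obtained at each time point listed", so both are to be collected. Footnote b to the table says that "12-lead ECGs will be extracted from the Holter recorded flashcards in triplicate within a 10-minute window". It is attached to the 0 h entry and to every later ECG entry, but not to −1.0 h. The running text makes no such exception: Protocol 5.6 describes serial ECGs as triplicate, and Protocol 8.4.6 says "Triplicate measurements of each serial ECG will be used to obtain an average value for each time point".

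**Bands.** Protocol 8.4.6 and SAP 7.6.7 tabulate QTcF as ≤450 msec and then "451- 480 msec, 481- 500 msec, > 500 msec". The change is tabulated as ≤30, 31–60 and >60 msec.

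**Discontinuation limit.** Protocol 4.6.1.1 lists "QTcF ≥ 500 msec confirmed by at least one repeat ECG" as a reason to discontinue. Table 4.6.1.2-1 uses the same threshold.

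**The concern.** Every ΔQTcF value, the 90% confidence interval at each time point and the regression on concentration all depend on the baseline. If its definition fits two scheduled readings, two programmers can derive different changes from the same data, and the choice could be made after the data are seen. The serial subset may be as small as 15 subjects per dose, so any precision available from a second pre-dose reading is worth having.

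The bands raise a separate issue. The tabulated quantity is an average of three readings, so it need not be a whole number, yet the categories are written for whole milliseconds. Some values then belong to no category and the table need not add up to its denominator.

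**Working it through.** The documents give no SD, precision target or sample-size rationale for the ECG analysis, so there is no stated figure to reproduce. All variances below are assumptions.

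**1. Effect of the baseline rule**

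Let s² be the error variance of a triplicate mean at one time point.

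- One baseline time point: Var(change) = s²(1 + 1) = 2s².
- Mean of two triplicate baselines whose errors have correlation ρ: Var(change) = s²[1 + (1 + ρ)/2].
- SD ratio = √{[1 + (1 + ρ)/2]/2}. For ρ = 0 it is √(1.5/2) = 0.866; for ρ = 0.5, 0.935; for ρ = 0.8, 0.975. The reductions are about 13%, 6% and 3%.
- True between-subject variation in the change also dilutes the gain. With assumed s = 6 and t = 8 msec, the ratio is √[(1.5×36 + 64)/(2×36 + 64)] = √(118/136) = 0.931, a 7% reduction even at ρ = 0.

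**2. If −1.0 h is a single tracing**

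Write the variance of a single tracing as a + b = 1, where a is shared by tracings at the same time point and b is replicate noise. A triplicate mean then has variance a + b/3. Errors at different time points are taken as independent.

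| b | Ratio, two time points weighted equally | Ratio, mean of all four tracings (weights 3/4 and 1/4) |
|---|---|---|
| 0 | 0.866 | √[(1 + 0.625)/2] = 0.901 |
| 0.5 | 0.901 | √[(0.667 + 0.4375)/1.333] = 0.910 |
| 1 | 1.000 | √[(0.333 + 0.25)/0.667] = 0.935 |

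Equal weighting of the two time points can therefore gain nothing. Averaging over tracings avoids that case.

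**3. Size on the confidence interval**

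The 90% half-width with n = 15 is t(0.95, 14) × SD/√15. In the best case (ratio 0.866):

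- assumed SD 8 msec: 3.64 falls to 3.15;
- SD 10: 4.55 falls to 3.94;
- SD 15: 6.82 falls to 5.91.

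**4. Values in no band**

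If single readings are whole milliseconds, triplicate means are multiples of 1/3. As written, 450.33, 450.67, 480.33 and 480.67 have no QTcF band, and changes of 30.33 and 30.67 have no change band. There is no gap at 500 or at 60.

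The chance of falling in one gap is about (2/3) × the normal density at its midpoint. The counts use 30 subjects × 6 footnoted time points = 180 QTcF values, and 30 × 5 = 150 changes.

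- QTcF, assumed mean 410–430 and SD 15–25 msec: 0.05% to 0.9%, or 0.1 to 1.6 values of 180.
- Change, assumed mean 0–10 and SD 8–15 msec: 0.002% to 0.7%, or 0 to 1.0 values of 150.

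**5. The 500 msec boundary**

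A mean of exactly 500.0 falls in the 481–500 band and also meets the ≥500 limit; 500.33 falls in >500. Under the same assumptions, the chance that a mean is exactly 500.0 is at most about 1 in 10,000.

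**The case against.** **Baseline.** The natural reading is that baseline means the 0 h row. That row is labelled pre-dose, has the paired PK draw and carries the triplicate footnote, whereas −1.0 h has neither. Section 8.2 of the Phase 1 SAP appendix also takes the last value before first dose. This is a fair argument for what was probably intended. It does not settle the expansion cohort, because that rule sits in the Phase 1 plan and Protocol 5.6 and 8.4.6 treat serial ECGs as triplicate without exception.

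A reader might infer that the plan discards the −1.0 h ECG, or that each change rests on one noisy tracing. The documents support neither. Nothing says −1.0 h is dropped, and the 0 h value is already a mean of three. A reader might also count the gain as a free third more subjects (2/1.5 = 1.33). That needs triplicate extraction at −1.0 h, independent errors an hour apart and no true variation between subjects in the change.

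**Bands.** Whole-millisecond notation is common, and rounding would close every gap. SAP sections 8 and 9 refer to a data presentation plan for conventions and outputs, and it may contain a rounding rule. That is possible, but the bands as stated are incomplete for averaged data. The Phase 1 SAP (7.6.6) used >450 and >30 as lower limits, with no gap at those two points.

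**500 msec.** It is tempting to say that the table misses the stopping limit. It does not implement that limit. Discontinuation is an individual rule needing a repeat ECG, while the table describes averaged Holter values at scheduled times. The ECG listing with flagged abnormalities and the summary of AEs leading to discontinuation are separate outputs.

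**Conclusion.** The point holds as a minor specification gap. The baseline of the primary ECG endpoint is not uniquely defined against the schedule, and the plan contradicts itself on whether the −1.0 h ECG is triplicate. The precision at stake is an SD reduction between 0 and about 13%. The upper end assumes two triplicates with independent errors, and no variance in the documents supports any one value in that range. The category gaps are real but would affect about 0–2 values. The 500 msec difference matters only at exactly 500 and is a matter of reporting.

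These are descriptive analyses for a secondary objective in a study with no formal hypothesis, so no decision rule depends on them. The reason to act is that the wording can be settled before analysis at almost no cost.

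**What to change.** - In SAP 4.2, and in Protocol 8.4.6 if it is amended, define baseline as the mean of all available pre-dose Cycle 1 Day 1 serial ECG tracings.
- State whether the −1.0 h ECG is extracted in triplicate, so that footnote b agrees with Protocol 5.6 and 8.4.6.
- Use continuous bands: QTcF ≤450, >450–480, >480–500, >500; change ≤30, >30–60, >60. Averaging more tracings makes fractional values more common, so this change belongs with the first.
- Reconcile the >500 reporting band with the ≥500 threshold in Protocol 4.6.1.1 and Table 4.6.1.2-1, or state that they serve different purposes. The bands above keep the plan's existing top cut and take no position on the clinical limit.

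The cost is a few lines of wording. The one possible extra is a small number of vendor extractions if −1.0 h is not already read in triplicate. No new visits, samples or subjects are needed.

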8.4.8 Outcomes Research Analyses

Not applicable.

8.4.9 Other Analyses

HCT-CI scores will be summarized at baseline and at end of treatment.

Cytogenetic and molecular results will be summarized at baseline only.

8.5 Interim Analyses

For the dose expansion cohort, an interim assessment of safety will be assessed by Sponsor or designee on the first 6 patients treated on the 1000 mg ulocuplumab/LDAC combination arm. These must have had an opportunity for at least 28 days of follow-up. The review will be based all available safety data including DLTs reported during the first 28 days of follow-up. Randomization to the 1000 mg ulocuplumab combination arm will be suspended until the safety review is complete. Randomization to the other 2 arms will continue on a 1:1 basis until a decision is reached to resume randomization to all 3 arms.

In addition, an interim analysis of efficacy and safety will be conducted when 60 patients (i.e., 50% of the sample size) will have had an opportunity for 2 months of treatment and follow-up.

9 STUDY MANAGEMENT

9.1 Compliance

9.1.1 Compliance with the Protocol and Protocol Revisions

The investigator should not implement any deviation or change to the protocol without prior review and documented approval/favorable opinion of an amendment from the IRB/IEC (and if applicable, also by local health authority) except where necessary to eliminate an immediate hazard(s) to study subjects.

If a deviation or change to a protocol is implemented to eliminate an immediate hazard(s) prior to obtaining IRB/IEC relevant approval/favorable opinion(s), the deviation or change will be submitted as soon as possible to:

- IRB/IEC
- Regulatory Authority(ies), if applicable by local regulations per national requirements

Documentation of approval/favorable opinion signed by the chairperson or designee of the IRB(s)/IEC(s) and if applicable, also by local health authority, must be sent to BMS.

If an amendment substantially alters the study design or increases the potential risk to the subject: (1) the consent form must be revised and submitted to the IRB(s)/IEC(s) via the head of the study site for review and approval; (2) the revised form must be used to obtain consent from subjects currently enrolled in the study if they are affected by the amendment; and (3) the new form must be used to obtain consent from new subjects prior to enrollment.

If the revision is done via an administrative letter, BMS must inform the IRB(s)/IEC(s).

9.1.2 Monitoring

Representatives of BMS must be allowed to visit all study site locations periodically to assess the data quality and study integrity. On site they will review study records and directly compare them with source documents, discuss the conduct of the study with the investigator, and verify that the facilities remain acceptable. Source documents are defined as follows: screening log, subject identification code sheet, medical records, written informed consent, and study drug management sheets. Certain CRF pages and/or electronic files may serve as the source documents: such as the investigator assessment of efficacy.

In addition, the study may be evaluated by BMS or designee, internal auditors and government inspectors who must be allowed access to CRFs, source documents, other study files, and study facilities. BMS audit reports will be kept confidential.

The investigator must notify BMS promptly of any inspections scheduled by regulatory authorities, and promptly forward copies of inspection reports to BMS or designee.

9.1.2.1 Source Documentation

The Investigator is responsible for ensuring that the source data are accurate, legible, contemporaneous, original and attributable, whether the data are hand-written on paper or entered electronically. If source data are created (first entered), modified, maintained, archived, retrieved, or transmitted electronically via computerized systems (and/or any other kind of electronic devices) as part of regulated clinical trial activities, such systems must be compliant with all applicable laws and regulations governing use of electronic records and/or electronic signatures. Such systems may include, but are not limited to, electronic medical/health records (EMRs/EHRs), adverse event tracking/reporting, protocol required assessments, and/or drug accountability records.

When paper records from such systems are used in place of electronic format to perform regulated activities, such paper records should be certified copies. A certified copy consists of a copy of original information that has been verified, as indicated by a dated signature, as an exact copy having all of the same attributes and information as the original.

9.2 Records

9.2.1 Records Retention

The investigator (or head of the study site in Japan) must retain all study records and source documents for the maximum period required by applicable regulations and guidelines, or institution procedures, or for the period specified by BMS or designee, whichever is longer. The investigator (or head of the study site in Japan) must contact BMS or designee prior to destroying any records associated with the study.

BMS or designee will notify the investigator (or head of the study site in Japan) when the study records are no longer needed.

If the investigator withdraws from the study (eg, relocation, retirement), the records shall be transferred to a mutually agreed upon designee (eg, another investigator, study site, IRB/IEC). Notice of such transfer will be given in writing to BMS or designee.

9.2.2 Study Drug Records

Records for IP must substantiate IP integrity and traceability from receipt, preparation, administration, and through destruction or return. Records must be made available for review at the request of BMS/designee or a Health Authority.

If...	Then...

Supplied by BMS (or its vendors):
	
 • and guidelines and should include: • amount received and placed in storage area • amount currently in storage area • label identification number or batch number • amount dispensed to and returned by each subject, including unique subject identifiers • amount transferred to another area/site for dispensing or storage • nonstudy disposition (eg, lost, wasted) • amount destroyed at study site, if applicable • amount returned to BMS • retain samples for bioavailability/bioequivalence, if applicable • dates and initials of person responsible for Investigational Product dispensing/accountability, as per the Delegation of Authority Form.

Sourced by site, and not supplied by BMS or its vendors (examples include IP sourced from the sites stock or commercial supply, or a specialty pharmacy)
	
The investigator or designee accepts responsibility for documenting traceability and study drug integrity in accordance with requirements applicable under law and the SOPs/standards of the sourcing pharmacy.
 
These records should include:
 
 • label identification number or batch number • amount dispensed to and returned by each subject, including unique subject identifiers • dates and initials of person responsible for Investigational Product dispensing/accountability, as per the Delegation of Authority Form.

BMS or designee will provide forms to facilitate inventory control if the investigational site does not have an established system that meets these requirements.

